12.2 DEFINITION OF FEASIBILITY

The primary objective is to determine the feasibility of identifying actionable alterations (candidate to receive a matched therapy recommendation) in pediatric patients with recurrent/refractory leukemia (Cohort 1). A patient is defined to be a candidate to receive a matched therapy recommendation if (1) there is a sufficient leukemia/DNA specimen of acceptable quality for a complete RHP or gene fusion assay (profiling data), and (2) an actionable alteration is identified. It is estimated that 10% of enrolled patients are expected to lack sufficient profiling data and will be considered technical failures. Next generation sequencing for AML samples

identified mutations in approximately 30% of samples³³, however, large-scale assessment for oncogenic mutations for recurrent/refractory/high risk leukemias have not been performed. As a result, it is conservatively estimated that 15% of leukemia samples that are not technical failures will have an actionable alteration. The predicted proportion of enrolled patients who would have profile data and an actionable alteration is 13.5%. Therefore, this study will be considered feasible if at least 13% of participants have profile data and identifiable actionable alterations.

A total of 100 eligible patients will be enrolled to Cohort 1 for this feasibility study. With 100 eligible patients, the 90% exact binomial confidence interval (CI) will be within $\pm 8.6\%$. The following table displays the exact 90% binomial CI for identifiable actionable alterations under various scenarios.

No. with identifiable actionable alterations	% (90% exact CI)
6	6.0% (2.6-11.5%)
7	7.0% (3.3-12.7%)
8	8.0% (4.0-13.9%)

With 100 patients, at least 8 patients need to have profiling data and an identifiable actionable alteration to have the upper bound of the 90% CI covering 13%. Therefore, identifying actionable alterations in pediatric patients with recurrent/refractory leukemia will be considered feasible if at least 8 of 100 patients have identifiable actionable alterations.

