12 DATA ANALYSIS AND STATISTICAL CONSIDERATIONS

12.1 ACCRUAL

The feasibility rule described below requires at most 100 eligible Cohort 1 patients. After feasibility is established, an additional 100 Cohort 1 patients will be accrued to further describe the actionable mutations in disease type (specifically AML and ALL). Given increased access to CLIA fusion panel testing and research RNASeq, Cohort 1 accrual will be increased by 50 patients to further describe actionable mutations that can be found using fusion testing, and describe the alterations that are detected by RNASeq but may be missed in targeted panel assessment. Approximately 10-15 patients with recurrent / refractory leukemia, 5-10 patients with newly diagnosed AML (excluding APL), and 2-3 patients with rare leukemias are evaluated per year the DF/CHCC. Almost all of these patients receive ongoing care at the DF/CHCC. Because additional procedures are not required for enrollment onto the study and given our department previous success with enrolling patients on similar trials, we anticipate that the proportion of eligible subjects who consent to enrollment will be about 90% resulting in, on average, 11 eligible, enrolled subjects per year for Cohort 1 and 10 eligible patients for Cohort 2 at DF/CHCC. The collaborating sites, Columbia University Medical Center, Children's Hospital of Philadelphia, Children's Hospital at Montefiore, Johns Hopkins Children's Center, Seattle Children's Hospital, Children's Hospital Colorado, University of California, San Francisco, University of Chicago, Children's Hospital of Wisconsin, Memorial Sloan-Kettering Cancer Center, Children's Healthcare of Atlanta, and Children's Hospitals and Clinics of Minnesota anticipate a combined enrollment of at least 40 eligible patients per year for Cohort 1. If a patient on Cohort 2 develops refractory/relapsed disease, the patient will be changed to Cohort 1. Overall, the accrual rate will be approximately 50 Cohort 1 patients per year, and enrollment of 350 eligible patients can be completed in about 5 years. Patients will only be enrolled on Cohort 1 during this time, with patients already enrolled on Cohort 2 remaining in follow-up.

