12.4 ASSESSMENT OF STUDY OBJECTIVES

12.4.1 Primary Objective

Feasibility of identifying an actionable alteration will be addressed by the feasibility definition outlined in section 12.2. The observed rate of patients with actionable alterations, out of all patients enrolled to cohort 1, will be reported with a 90% confidence interval. The rate of patients with actionable alterations in Cohort 2 will be similarly reported.

The observed rate of patients with actionable alteration for the ALL and AML subgroups in Cohort 1 will be estimated along with a 90% confidence interval. Based on previous enrollment, it is estimated that 94, 15, and 72 out of the planned 200 Cohort 1 patients will have relapsed/refractory B-ALL, T-ALL, and AML, respectively. The remaining 19 are expected to have other rare leukemias. The width of the 90% exact confidence interval will be no larger than 17.9%, and 20.5% for relapsed/refractory B-ALL and AML, respectively. The rate of actionable mutations in relapsed/refractory T-ALL and other rare leukemias will be described. Additionally, it is estimated that 67 newly diagnosed AML Cohort 2 patients will be enrolled by the time Cohort 1 completes accrual. The width of the 90% exact confidence interval will be no larger than 23.5% for newly diagnosed AML.

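### Section 12.2 words feasibility both as at least 13% of participants and as at least 8 of 100; read literally the two disagree for 8 to 12 of 100, and meeting the second shows only that 13% is not excluded

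*Combined protocol and SAP*

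**What the plan says.** Section 12.2 builds its rule in steps. It assumes 10% technical failures and a 15% actionable rate in the remaining samples, and concludes: "The predicted proportion of enrolled patients who would have profile data and an actionable alteration is 13.5" per cent. From this it draws a first criterion: "this study will be considered feasible if at least 13% of participants have profile data and identifiable actionable alterations". It then fixes 100 eligible Cohort 1 patients, tabulates exact 90% binomial intervals for 6, 7 and 8 patients, and notes that at least 8 are needed "to have the upper bound of the 90% CI covering 13" per cent. From that it draws a second criterion: identifying actionable alterations "will be considered feasible if at least 8 of 100 patients have identifiable actionable alterations".

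Two other places depend on this section. Section 12.4.1 says: "Feasibility of identifying an actionable alteration will be addressed by the feasibility definition outlined in section 12.2". Section 12.1 says "The feasibility rule described below requires at most 100 eligible Cohort 1 patients", and makes the outcome the trigger for more enrolment: "After feasibility is established, an additional 100 Cohort 1 patients will be accrued".

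**The concern.** The same decision phrase is attached to two thresholds. The first is worded as a share of participants, which a reader would naturally apply to the observed proportion: 13 or more of 100. The second passes at 8. Section 12.4.1 sends the primary objective to section 12.2 without saying which of the two it means.

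The second criterion also rests on the upper confidence limit. A rule of that kind guards against wrongly declaring infeasibility. It does not show that the benchmark has been attained. If the result is reported simply as feasible, next to a sentence that equates feasible with at least 13%, readers may take 8 of 100 as evidence for a rate of 13% or more.

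At stake is the meaning of the primary conclusion. The study is non-therapeutic, so the harm is to the claim and not to patients. But section 2.3 says that a feasible result could lead to studies of efficacy, so what feasible means should be clear.

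**Working it through.** **Inputs, all from section 12.2:** n = 100; 10% technical failures; 15% actionable among the rest; benchmark 13%; cutoff 8; exact 90% binomial interval (5% in each tail).

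**1. Predicted rate.** 0.90 × 0.15 = 0.135, which matches the plan's 13.5%.

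**2. The plan's intervals and cutoff.** For x of n, the Clopper-Pearson lower limit is the 5% quantile of Beta(x, n − x + 1) and the upper limit is the 95% quantile of Beta(x + 1, n − x).

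| x of 100 | Recomputed 90% CI | Plan |
|---|---|---|
| 6 | 2.64–11.50% | 2.6–11.5% |
| 7 | 3.33–12.75% | 3.3–12.7% |
| 8 | 4.04–13.97% | 4.0–13.9% |

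The last upper limit appears to have been truncated rather than rounded, which does not matter. Seven of 100 excludes 13% and 8 of 100 does not, so 8 is the smallest count whose upper limit covers 13%. The cutoff is correctly derived.

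**3. Where the two criteria differ, with 13% read as an observed proportion.**

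| Result of 100 | At least 13% | At least 8 |
|---|---|---|
| 7 or fewer | not feasible | not feasible |
| 8 to 12 | not feasible | feasible |
| 13 or more | feasible | feasible |

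**4. How likely the disputed range is.** With X ~ Binomial(100, p), P(8 ≤ X ≤ 12) = P(X ≥ 8) − P(X ≥ 13).

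| True rate p | P(X ≥ 8) | P(X ≥ 13) | P(8 to 12) |
|---|---|---|---|
| 13% | 0.957 | 0.545 | 0.412 |
| 13.5% | 0.968 | 0.602 | 0.366 |
| 18% | 0.999 | 0.929 | 0.070 |
| 20% | 1.000 | 0.975 | 0.025 |

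The 13% and 13.5% are the plan's figures. The 18% and 20% are assumptions, included because the plan calls its 15% input conservative.

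**5. What passing shows.** At 8 of 100 the interval runs from 4.0% to 14.0%: 13% lies inside it, and so do rates far below 13%. The error that the rule limits is P(X ≤ 7 | p = 13%) = 1 − 0.957 = 0.043, a false declaration of infeasibility. For the lower 90% limit to reach 13%, 20 of 100 would be needed (13.7–27.7%); 19 of 100 gives a lower limit of 12.8%.

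**The case against.** The best reply is that the governing rule can be identified. Section 12.2 moves from a prediction to a benchmark, then to a sample size, a table of intervals and a count introduced as the consequence. Section 12.1 speaks of a single rule needing at most 100 patients, and only the count criterion is expressed out of 100. If 13% is a benchmark for the true rate, the derivation makes sense and there is no contradiction. The upper-limit basis and the interval at 8 of 100 are both printed, and nowhere does the plan say that 8 of 100 demonstrates 13%.

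Much of this stands. It is the more sensible reading, and the cutoff should stay. But the plan never calls 13% a target or benchmark. It uses the same decision wording for both, and section 12.4.1 does not choose between them. The reply also leaves untouched what passing can show.

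It is equally fair that the 37% depends on a prediction the plan calls conservative; the probability falls quickly at higher true rates.

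A reader might go further and infer that the patient sets conflict, since section 12.1 adds 100 patients and then "Cohort 1 accrual will be increased by 50 patients", while section 12.4.1 reports the rate over all of Cohort 1. The documents do not support that. Applying the rule to 100 patients and estimating the rate in the whole cohort are separate tasks, and nothing reapplies the cutoff to the larger group.

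**Conclusion.** The point holds as a defect in how the primary decision rule is worded, worth correcting before the result is reported. The literal conflict covers exactly 8 to 12 of 100, with probability 37% at the plan's predicted rate and 41% at 13%, and much less if the true rate is 18% or higher. These figures assume independent patients with a common rate, and that the 13% sentence is applied to the observed proportion. Whichever reading is taken, a result at the cutoff supports only the statement that the 90% interval does not exclude 13%.

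Two stronger conclusions should be resisted. The cutoff of 8 is not miscalculated; it follows from the stated upper-limit criterion. Nor can the rule be said to exceed an allowed false-positive rate, because the plan names no unacceptable rate against which to measure one.

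**What to change.** Keep the cutoff of 8 of 100 and change the wording of section 12.2.

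- Replace the sentence containing the 13% criterion with: *The target true rate is 13%.*
- Replace the final sentence with: *The feasibility criterion is met if at least 8 of the 100 eligible Cohort 1 patients enrolled for the feasibility assessment have profiling data and an actionable alteration; this means that the 90% exact CI does not exclude 13%, and does not establish a rate of 13% or more.*
- Add: *If 8 to 12 of these 100 patients have one, the report will state that the criterion is met and that the observed rate is below the 13% target.*
- Report the full Cohort 1 rate with its 90% interval, as section 12.4.1 already plans, as the main estimate of the rate, without reapplying the 8 of 100 rule to it.

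Cutoff, sample size, data collection and the chance of passing are unchanged. The cost is a more modest claim. At the plan's predicted 13.5% there is a 37% chance that the report must say that the criterion was met with an observed rate below target.

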12.3 EFFICACY

Response will be assessed only in those participants receiving treatment according to the matched therapy recommendation. Bone marrow or other assessments to monitor response to the treatment will be performed at the discretion of the treating oncologist. Response will be determined by report from the participants' treating oncologists via data collection from chart review at the participant's institution and query of the treating oncologist/site PI. The proportion of participants receiving therapy according to the matched therapy recommendation with a partial or complete response while receiving therapy based on the recommendation will be determined. The proportion of responders will be compared to the 10% reported response rate in all pediatric phase I trials because the participant population is similar to that enrolled on phase I trials⁴².

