7 REQUIRED DATA

7.1.1 At Study Enrollment:

- Participant identifiers including name, medical record number, date of birth, gender, race, ethnicity.
- Diagnosis, including immunophenotype, cytogenetics, FISH studies
- Date of enrolling diagnosis
- Status (recurrent or refractory leukemia)
- Prior treatment and response to treatment (especially targeted therapy)
- Any molecular/sequencing data obtained prior to enrollment
- Treating oncologist's name and contact information

7.1.2 Following matched therapy treatment recommendation:

- For all patients enrolled with recurrent, or refractory disease (Cohort 1)
 - Every four months: vital status, disease status, any anti-leukemia treatment(s) received since the last assessment
- For all patients with newly diagnosed high-risk disease without recurrence (Cohort 2):
 - Every six months: vital status, disease status, any anti-leukemia treatment(s) received since the last assessment
- For participants who received a matched therapy recommendation:
 - If the recommendation was not used, a query of the site PI will be performed to assess barriers to receiving the matched therapy recommendation (e.g., Provider did not agree with recommendation, drug not available, insurance denied coverage, drug not available in correct formulation, patient unable to tolerate, progressive disease, etc). Site PI response may involve contacting the treating oncologist or a limited chart review.
- For participants who receive treatment according to the matched therapy recommendation:
 - Data from chart review of the medical participant's records at the participating institutions and query of primary site PI will document dates of treatment initiation, best response to treatment,

date of best response, and date of progression while receiving treatment based on the matched therapy recommendation.

- Participants will be followed until death or for 5 years from the time of study enrollment.
- Required data will be collected using case report forms.

REQUIRED DATA

	ALL PATIENTS		Cohort 1: recurrent or refractory leukemia or MDS	Cohort 2: newly-diagnosed high-risk leukemia/MDS	ALL PATIENTS
	Screening	Enrollment	Every 4 Months after MTT Report	Every 6 Months after Enrollment	At Time of Disease Progression
Baseline Demographics ^A	X				
Pathology Report	X				X
Molecular/sequencing data previously obtained or obtained outside of this study		X			X
Vital Status			X	X	
Disease status:		X	X	X	X
Interval anti-leukemia treatment received			X	X	X

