9.3 RECOMMENDATION FOR A MATCHED TARGETED THERAPY

9.3.1 Formulation of Recommendation

The Principal Investigator or one of the Pediatric Oncology Co-Investigators will utilize clinical data and the interpreted profiling data to create a treatment recommendation matched to the identified genomic alteration. As the basis for the recommendation, actionable alterations will be determined from analysis from RHP and fusion gene testing as well as any molecular/sequencing data obtained in a CLIA- and / or CAP-certified laboratory prior to enrollment. Considerations taken into account in determining the recommendation will include: IC₅₀ of a particular drug against the particular mutation identified; available drug formulations; prior therapies received; participant age and availability of data regarding a pediatric dose; side effect profiles; availability of phase I/II trials. The recommendation will be tiered according to the strength of evidence for the specific genomic alteration in leukemia, or cancer in general (Appendix 1). Additional tiering will be applied for drug availability (Appendix 2).

9.3.2 Review and Approval of Genomic Alteration and Matched Treatment Recommendation by Expert Panel

The recommendation will be reviewed and approved by a panel composed of experts from pediatric oncology, developmental therapeutics, and cancer biology. The Expert Panel will meet twice a month either in person or by conference call. Conference call-in information will be provided to the Expert Panel members to allow for travel, scheduling conflicts and to include members from all participating sites. Members of the panel will be available to the investigators for consultation during creation of the recommendation as needed.

9.3.3 Communication of Genomic Alteration and Matched Treatment Recommendation to Study Participants and Their Physician

For participants with AML, MDS, rare or other high-risk leukemia who have not had a relapse, the leukemia profiling results will be released at the time of profiling. The expert panel will address in their letter communicating results and recommendation clearly distinguish recommendations which could be considered to be acted on during upfront therapy (which are expected to be few) and those that could be considered to be acted on only at the time of non-response to standard therapy or disease recurrence.

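### Section 12.3 measures response in everyone who receives the matched therapy but neither requires nor records active disease when it starts, so patients already in remission can push the rate up or down

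*Combined protocol and SAP*

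**What the plan says.** **Denominator.** Section 12.3: "Response will be assessed only in those participants receiving treatment according to the matched therapy recommendation". It sets no condition on disease state and no restriction to one cohort.

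**Numerator.** Section 12.3 counts treated participants "with a partial or complete response while receiving therapy based on the recommendation will be determined". It names no response criteria and gives no rule for a patient who has no detectable leukemia at the first dose.

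**Assessment.** "Bone marrow or other assessments to monitor response to the treatment will be performed at the discretion of the treating oncologist". The result is then taken from clinical records and queries: "Response will be determined by report from the participants' treating oncologists via data collection from chart review at the participant's institution".

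**Benchmark.** "The proportion of responders will be compared to the 10% reported response rate in all pediatric phase I trials". The stated reason is that the two populations are alike.

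**Data collected.** For participants who take the recommended therapy, section 7.1.2 will "document dates of treatment initiation, best response to treatment", together with the date of best response and the date of progression. Disease status at the start of that therapy is not on the list. In the required-data table, disease status is due at enrollment, at the 4-month (Cohort 1) or 6-month (Cohort 2) contacts, and at progression. None of these is tied to the first dose.

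**Use outside relapse.** Section 9.3.3 has the expert panel's letter separate recommendations that might be used during upfront therapy, which it expects to be few, from "those that could be considered to be acted on only at the time of non-response to standard therapy or disease recurrence".

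**The concern.** A response rate for a leukemia therapy is interpretable only if the patients had leukemia to respond when the therapy began. A patient who enrolls at relapse, is reinduced while profiling and panel review proceed, reaches remission and then starts the matched drug is in complete remission while receiving it. On a literal reading of 12.3 that patient can be scored as a responder, although earlier chemotherapy produced the remission. Another oncologist might report no response for the same patient, because nothing changed on the drug, and the patient would remain in the denominator. The plan does not choose between these.

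The comparison with 10% is what is at stake. It is justified by similarity to patients on phase I trials, and nothing in 12.3 secures that similarity at the point where treatment starts. Section 6.1 makes determining response one of the purposes of data collection, and section 2.3 says that outcomes in treated participants will be used to explore whether the approach might affect outcome. The rate is therefore likely to be read and cited even though it is a minor analysis.

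**Working it through.** **Is a start in remission plausible under this protocol?** These provisions, set side by side, suggest that it is:

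- Section 4.1.4 admits patients on stored specimens or on an existing clinical Rapid Heme Panel result. Sections 4.1 and 4.2 do not require active disease on the day of enrollment.
- A recommendation follows profiling and review by a panel that meets twice a month (9.3.2). Section 7.1.2 expects anti-leukemia treatment to be given between contacts.
- Section 9.3.3 allows some upfront use, and 12.3 does not exclude Cohort 2.
- Section 8.1.2 makes a morphologically confirmed remission marrow the preferred germline sample, so documented remissions are expected in some participants.

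None of these gives a frequency.

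**Inputs.** Section 12.3 states no sample size, alpha or power. Its only figure, 10%, comes from a cited source, so the plan has no calculation to reproduce. The illustration uses:

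- p = 0.10, the true response rate in patients with active disease, set equal to the benchmark in 12.3;
- f, the share of treated patients in remission at start (assumed);
- s, the share of those patients who are scored as responders (unstated in the plan, so anywhere from 0 to 1).

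**Formula.** Reported rate = s·f + (1 − f)·p. The bias is f·(s − p), so the rate is unbiased only if f = 0 or s happens to equal p.

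| f (assumed) | all scored responders (s = 1) | all scored non-responders (s = 0) | excluded |
|---|---|---|---|
| 5% | 0.05 + 0.95 × 0.10 = 14.5% | 0.95 × 0.10 = 9.5% | 10% |
| 10% | 0.10 + 0.90 × 0.10 = 19% | 0.90 × 0.10 = 9% | 10% |
| 20% | 0.20 + 0.80 × 0.10 = 28% | 0.80 × 0.10 = 8% | 10% |
| 30% | 0.30 + 0.70 × 0.10 = 37% | 0.70 × 0.10 = 7% | 10% |

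**The same in patients.** Take 20 treated participants (assumed), 4 of them in remission at start. The 16 with active disease yield 16 × 0.10 = 1.6 expected responders. The reported rate is (1.6 + 4)/20 = 28%, or 1.6/20 = 8%. With the 4 set aside it is 1.6/16 = 10%.

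**Effect on the comparison with 10%.** Section 12.3 attaches no test, so this step is illustrative only. Assume an exact one-sided 5% rule with n = 20; the cut-off is then 5 or more responders. The chance of crossing it is 4.3% at a rate of 10%, 70% at 28% and 1.8% at 8%. The first figure applies with 20 evaluable participants, all with active disease at start.

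**The case against.** The strongest reply is that 12.3 should be read with its neighbours. Section 6.1 speaks of response to the recommended treatment, and 7.1.2 of best response to treatment with its date. In ordinary usage a remission that predates the drug is not a response to it. The required-data table also has rows for interval anti-leukemia treatment and for response to it, and its footnote B queries sites on examination, laboratory and marrow findings. A remission after reinduction would therefore often be on file, the matched-therapy start date is collected, and chart review could often establish status at that date. Few upfront uses are expected, and Cohort 2 patients who relapse move to Cohort 1 (12.1). The study is non-therapeutic, and response has no decision rule.

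Much of this stands, and it limits the point. Four stronger readings are tempting, and the documents do not support them:

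- *Patients in remission are counted as responders.* No section says so. The plan is silent, and reliance on the treating oncologist's report does not by itself turn a remission into a response.
- *The bias always runs upward.* Keeping these patients as non-responders lowers the rate.
- *The problem cannot be repaired afterwards.* Retrospective chart review could often recover status at start. It is likely to be harder with 4- or 6-month spacing, and for participants outside the sites, whose data arrive on mailed or emailed forms (7.2). The form in Appendix 21 was not in the text reviewed, so its fields could not be checked.
- *The response proportion is invalid.* That would need a known, material share starting in remission, and none is given.

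The objection does not remove the gap. The evaluable set is undefined, classification rests with each oncologist, and the one status needed to settle it is not a listed data item. Study-team assignment of response and disease-specific criteria would be further choices; this point does not require them.

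**Conclusion.** The point holds as a gap in the definition of the response-evaluable set and in the data collected to support it. With the denominator as written, any patient in remission at the start of matched therapy distorts the rate if scored uniformly as a responder or as a non-responder. At an assumed 10% starting in remission, a true 10% could be reported as anything from 9% to 19%; at 20%, from 8% to 28%. These ranges rest on assumed shares and on a true rate equal to the benchmark. The documents give neither the share in remission nor the number treated.

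The consequence is confined to the 12.3 response proportion and its comparison with 10%. Response is not among the primary, secondary or exploratory objectives in section 3, and the feasibility rule of at least 8 of 100 in section 12.2 is untouched. The change should be made, but the primary conclusion does not depend on it.

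**What to change.** - **Section 7.1.2 and its form:** for participants who start the recommended therapy, add disease status at start, and the last clinically obtained marrow or blood blast percentage before the first dose with its date.
- **Section 12.3:** restrict the response proportion, and its comparison with 10%, to participants with active disease at the start of matched therapy.
- **Section 12.3:** report participants who start in remission separately and descriptively, giving their number so that the reader can see the exclusion.
- **Participants already treated:** complete the new fields from the chart where possible, and report how many have unknown status at start.

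**Cost.** A few chart-review fields for the treated subset and a wording change. No new procedures are needed, because only assessments made for clinical care are abstracted. The denominator shrinks. In the example above it falls from 20 to 16, and the standard error at a 10% rate rises from √(0.09/20) = 6.7 points to √(0.09/16) = 7.5 points. That is a modest loss of precision for a rate that no longer depends on how patients in remission are labelled.

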2.3 POTENTIAL BENEFITS TO SUBJECTS AND/OR SOCIETY

While technological advances are resulting in ever increasing possibilities for tumor profiling, research paradigms for studying the clinical utility of large-scale leukemia genomic profiling and a matched targeted therapy approach to treatment in the setting of high risk/recurrent/refractory leukemia or rare subtypes without a clear treatment, are lacking. If a reasonable proportion of participants can receive a matched targeted therapy recommendation within this study we will demonstrate that, using the profiling technologies currently available,

a personalized approach to treatment is feasible in recurrent / refractory / high-risk leukemia in pediatric participants.

The result of this trial would have implications for continued development and testing of targeted therapy in pediatric patients. If this study is feasible, future studies could then be designed to more rigorously evaluate the efficacy of a personalized approach to leukemia therapy. Systematic identification of genetic alterations and identification of activated pathways will also inform development of future “basket trials” where several different therapies are offered under the umbrella of a single clinical protocol.

This will be the first attempt to broadly characterize the range of actionable alterations present in recurrent / refractory / high-risk pediatric patients with leukemia. The actionable alterations identified in this study and the follow-up laboratory investigation promoted by those results have the potential to add greatly to our understanding of the oncogenic mechanisms in recurrent / refractory / high-risk leukemia. This may help to inform future drug development and future clinical trials.

This study has the potential to help individual children enrolled on the trial who may potentially receive matched therapy based on the identified genomic alteration. Because we plan to follow the outcome of participants who receive treatment based on the therapy recommendation, we will be able to explore whether the type of personalized cancer therapy studied here has the potential to impact the outcome of pediatric participants with recurrent / refractory leukemias.

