4.0 ELIGIBILITY

4.1 INCLUSION CRITERIA

4.1.1 Age

Age birth to ≤ 30 years at study entry

4.1.2 Diagnosis: Patients will be enrolled in one of the two cohorts based on diagnosis:

Cohort 1: Relapsed/refractory leukemia

- Acute lymphoblastic leukemia, first or greater relapse
- Acute myeloid leukemia, first or greater relapse
- Leukemia refractory to induction chemotherapy
- Other recurrent leukemia
- Myelodysplastic syndrome (MDS), first or greater relapse, or refractory to initial therapy

Cohort 2: New diagnosis- closed to accrual as of 11/18/2019

- Acute myeloid leukemia, new diagnosis
- New diagnosis infant *MLL*-rearranged ALL or low hypodiploid (<40 chromosomes) ALL
- Rare leukemia- e.g., JMML, leukemia of ambiguous lineage
- Secondary leukemia
- Myelodysplastic syndrome (MDS)

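### The 10% phase I comparison in section 12.3 is not limited to relapsed/refractory participants, so never-relapsed Cohort 2 participants treated upfront can enter it

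*Combined protocol and SAP*

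**What the plan says.** Section 12.3 defines the response set by one condition: "Response will be assessed only in those participants receiving treatment according to the matched therapy recommendation". It determines the proportion with a partial or complete response while on that therapy, and then states: "The proportion of responders will be compared to the 10% reported response rate in all pediatric phase I trials". The justification is "because the participant population is similar to that enrolled on phase I trials". The section names no cohort, test, sample size or decision rule.

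Other sections bear on who can be in that set:

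- **Section 9.3.3** covers participants who have not relapsed. They receive results at the time of profiling, and the expert panel's letter is to distinguish "recommendations which could be considered to be acted on during upfront therapy (which are expected to be few") from those to be considered only after non-response or recurrence.
- **Section 7.1.2** sets its response collection by treatment received, not by cohort: "For participants who receive treatment according to the matched therapy recommendation", chart review and a site query "will document dates of treatment initiation, best response to treatment". The required-data table marks response to treatment for both cohorts.
- **Section 4.1.2** describes Cohort 2 (new diagnosis) as "closed to accrual as of 11/18/2019". Under section 12.1, those already enrolled stay in follow-up and move to Cohort 1 only if their disease relapses or becomes refractory.
- **Section 2.3** describes outcome follow-up as exploring whether personalized therapy "has the potential to impact the outcome of pediatric participants with recurrent / refractory leukemias".

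**The concern.** A benchmark taken from outside the study is only as good as the match between the two populations. Section 12.3 rests that match on similarity to phase I enrollees. A newly diagnosed participant treated upfront does not fit that description, yet meets the section's only entry condition. If such participants respond more often than 10%, a pooled proportion above 10% could partly reflect response to upfront therapy and be read as activity of matched therapy in relapsed or refractory disease. Unlike sampling error, this shift has a predictable direction.

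The neighbouring sections keep the cohorts apart: 12.2 restricts feasibility to Cohort 1 by name, and 12.4.1 reports the Cohort 2 rate of actionable alterations separately. Section 12.3 is the one that uses an external benchmark, and it makes no such separation.

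**Working it through.** **The plan's figure.** The 10% comes from a cited source. The documents give no inputs for it, so it cannot be reproduced. The question is which participants are compared with it.

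**Tracing one participant through the text.** Take a Cohort 2 participant with newly diagnosed AML, never relapsed, treated according to a recommendation during upfront therapy.

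1. Can this happen? Yes, under 9.3.3, though it is expected to be rare.
2. Is best response recorded? Yes, under 7.1.2 and the required-data table.
3. Does the participant move to Cohort 1? No. Section 12.1 moves only those with relapsed or refractory disease.
4. Does closing Cohort 2 to accrual remove the participant? No. Section 12.1 keeps those already enrolled in follow-up.
5. Does the participant meet the 12.3 condition? Yes.
6. Does the 12.3 rationale describe the participant? No.

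**Size (illustration only).** The documents give neither the number treated nor an upfront response rate. Assumptions:

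- n₁ treated Cohort 1 participants, responding at exactly 10%.
- k upfront-treated Cohort 2 participants, responding at q = 50% to 80%.
- n₁ = 10 and 20 are arbitrary. n₁ = 34 is a high case: section 12.2 predicts 13.5% of enrolled patients with an actionable alteration, and 0.135 × 250 = 33.75, where 250 = 100 + 100 + 50 Cohort 1 patients from section 12.1. It supposes that every candidate is treated.

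Expected pooled proportion = (0.10·n₁ + k·q) / (n₁ + k)

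Shift from 10% = [k / (n₁ + k)] × (q − 0.10)

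Worked case, n₁ = 20:

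- k = 1: (2 + 0.5)/21 = 11.9%; (2 + 0.8)/21 = 13.3%
- k = 2: (2 + 1.0)/22 = 13.6%; (2 + 1.6)/22 = 16.4%

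| n₁ (assumed) | k = 1, q = 50% to 80% | k = 2, q = 50% to 80% |
|---|---|---|
| 10 | 13.6% to 16.4% | 16.7% to 21.7% |
| 20 | 11.9% to 13.3% | 13.6% to 16.4% |
| 34 | 11.1% to 12.0% | 12.2% to 13.9% |

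**Against sampling error.** The exact (Clopper-Pearson) 90% interval for 2 of 20 is 1.8% to 28.3%. With n₁ = 20, the shifts of 1.9 to 6.4 percentage points are well inside it. No false-positive rate is calculated, because 12.3 states no test.

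**The case against.** The strongest reply is that nothing depends on this. The study is non-therapeutic, efficacy is not among its primary, secondary or exploratory objectives, and the feasibility rule in 12.2 ignores response. That stands, and it caps the importance of the point.

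The second reply is that the intent is visible. Section 2.3 speaks of recurrent and refractory disease, the phase I rationale points the same way, and section 6.1 ties Cohort 1 data collection to the recommendation but Cohort 2 collection to time since enrollment. This makes the intent a fair inference. It does not put it in 12.3, whose set is defined without restriction, and response is collected in both cohorts.

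Third, the affected group may be empty: upfront use is expected to be rare, Cohort 2 is closed to accrual, and relapsing participants move out of it. That also stands. The documents neither show such a participant nor rule one out, and every quantity in the illustration is assumed.

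Finally, limiting the set to Cohort 1 would not establish that 10% is the right comparator. Cohort 1 includes first relapse and disease refractory to induction, and 12.3 does not separate matched therapy given alone from matched therapy given with chemotherapy. This is correct. The change removes only the group for whom the rationale plainly fails.

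**Conclusion.** The concern holds on the text and is minor. As written, 12.3 would pool never-relapsed participants treated upfront with relapsed or refractory ones and compare the total with a rate justified only for the latter. If upfront response exceeds 10%, the error favours matched therapy.

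Under the assumed values, one or two such participants raise the expected proportion from 10% to between 11.1% and 21.7%. The upper end needs only 10 treated Cohort 1 participants, two upfront participants and 80% upfront response. No figure in the documents is contradicted, and the primary conclusion is unaffected. It is worth correcting because the correction is cheap.

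**What to change.** Amend 12.3 to state that:

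- The comparison with 10% is limited to Cohort 1. A participant moved from Cohort 2 counts only for matched therapy started after the move.
- Response in Cohort 2 participants treated according to a recommendation before relapse or refractory disease is reported separately, without the benchmark.

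Reporting the Cohort 1 proportion with an exact 90% interval, at the confidence level used in 12.4.1, would be a useful addition but is a separate matter.

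The cost is wording in one section and a slightly smaller comparison set. Cohort, treatment start date and best response are already collected. The date of the move to Cohort 1 is not itself listed in 7.1.2. It should be recoverable from the progression data in the required-data table, and the sponsor should confirm this.
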